4.3. Justification for Dose

4.3.1. Justification for E-602 Dose

The starting dose in this FIH study is based on the maximum safe starting dose based on the highest non-severely toxic dose (HNSTD) or the no-observed-adverse-effect level (NOAEL) from the preclinical Good Laboratory Practice (GLP) toxicology studies and data from *in vitro* human cytokine release assays. The dose increment between cohorts is based on a modified Fibonacci pattern. Details for each method to estimate starting dose can be found in the IB.

Since immune desialylation serves as both a critical pharmacodynamic indicator for the overall activity of E-602 and a logical surrogate marker for the potential of E-602 to cause immune-related toxicity, the EC₂₀ for E-602 desialylation of human CD8 T cells *in vitro* was estimated to be 15.5 μ g/mL and 14.4 μ g/mL for CD4 T cells (Table 1). Taken together, the EC₂₀ for immune cell desialylation is approximately 15 μ g/mL.

Table 1 50% And 20% effective concentrations (EC₅₀ and EC₂₀) of E-602 for desialylation of human CD8 and CD4 T cells

Protocol Number: PAL-E602-001

Version 8.0, 24 August 2023

	CD8+ T cells (µg/mL)	CD4+ T cells (µg/mL)
EC ₅₀	62.0	57.5
EC ₂₀	15.5	14.4

A human PK model was developed for E-602 based on the NHP data to estimate the amount of delivered E-602 that would yield a blood concentration of 15 μ g/mL at C_{max}. A range of 5 dose levels, 0.1, 0.5, 1, 1.5, and 3 mg/kg, were simulated to produce concentrations over a 21-day period, with weekly dose administration. The simulated concentrations of dose levels 1 and 1.5 mg/kg produced a C_{max} of 10 and 15 μ g/mL, respectively.

Thus, the human dose delivered that would likely produce the pharmacodynamic EC_{20} for desialylation of immune cells at the C_{max} would be approximately 1.5 mg/kg. Based on these data, the first cohort dose level will be 1 mg/kg.

An additional monotherapy dose escalation cohort of 30 mg/kg is planned for evaluation. As limited desialylation of peripheral immune cells has been observed at the 1 and 3 mg/kg dose levels, addition of 30 mg/kg dose level is expected to further inform the PK/PD relationship and identification of the recommended Phase 2 dose of E-602 monotherapy. The pharmacodynamic activity of E-602 in NHP GLP toxicology studies demonstrated a linear dose response of immune cell desialylation following E-602 administration across the dose range with maximum desialylation at 200 mg/kg (human equivalent dose of 60 mg/kg). The 30 mg/kg dose remains below the human equivalent dose (approximately 33 mg/kg) of the NHP NOAEL (100 mg/kg). Clinical experience (as of 23-September-2022) supports the tolerability of E-602 monotherapy. Doses up to 10 mg/kg of E-602 monotherapy have been evaluated with no DLTs reported and the 20 mg/kg E-602 monotherapy dose level is currently enrolling. Preliminary data indicate that the adverse events are consistent with an advanced cancer population. No E-602 related serious adverse events have been reported.

4.3.2. Justification for Cemiplimab Dose

A 350 mg Q3W dose of cemiplimab was chosen based on the safety and anti-tumor activity observed across >20 clinical studies (see cemiplimab IB). Analysis of the 350 mg Q3W dose regimen demonstrated that median steady-state concentrations (CV%) of cemiplimab ranged between a maximum concentration (C_{max,ss}) of 166 mg/L (28%) and a minimum concentration (C_{min,ss}) of 59 mg/L (48%). Cemiplimab exposure in serum at the fixed dose of 350 mg Q3W is similar to that at the body weight adjusted dose of 3 mg/kg once every 2 weeks (Q2W). The dose of 350 mg Q3W is consistent with the current USPI (Libtayo[®] USPI, 2022).

4.4. End of Study Definition

The end of the study is defined as the date of the last visit of the last subject in the study.

A subject is considered to have completed the study if he/she has completed the final study visit or follow-up contact, whichever is later.

5. Study Population

5.1. Inclusion Criteria

- 1. Criteria for each cancer type are as follows:
 - a. Melanoma:
 - Histologically confirmed unresectable Stage III or Stage IV cutaneous or mucosal melanoma.
 - Subject must have known BRAF genetic mutation status.
 - o BRAF mutation-positive subjects are eligible without prior treatment or after failure of BRAF directed inhibitor therapy.

Protocol Number: PAL-E602-001

Version 8.0, 24 August 2023

- Subjects must have had prior therapy with an anti-PD-(L)1 pathway therapy and been deemed resistant (had progression on therapy or within 3 months of discontinuation of therapy).

b. Ovarian:

- Histologically or cytologically confirmed diagnosis of advanced, epithelial ovarian cancer (except carcinosarcoma), primary peritoneal, or fallopian tube cancer.
- Subject has received at least 1 line of platinum-containing therapy or must be platinum-intolerant.
- A subject with homologous repair deficiency (HRD) positive disease may participate if he/she has received prior polyadenosine diphosphate ribose polymerase (PARP) inhibitor therapy.
- Subject has no standard therapy options that are likely to convey clinical benefit.

c. NSCLC:

- Histologically or cytologically documented Stage IV NSCLC not amenable to curative surgery or radiation.
- Subject must have progressed on standard therapy that includes platinum-based chemotherapy and anti-PD-(L)1 pathway therapy.
 - Subjects must have been deemed resistant (had progression on therapy or within 3 months of discontinuation of therapy) to an anti-PD-(L)1 therapy.
- Subjects with known active driver mutations that confer insensitivity to immune checkpoint inhibitors are excluded, including those with driver mutations in EGFR, ALK, ROS-1, and RET.

d. Colorectal cancer:

- Histologically or cytologically documented metastatic colorectal cancer.
- Subject must have been previously treated with chemotherapy regimens based on fluoropyrimidine, oxaliplatin, and irinotecan; and anti-VEGF biological therapy; and, if RAS wild-type, an anti-EGFR therapy.
- Subjects with microsatellite instability-high (MSI-H) or mismatch repair deficient tumors (dMMR) must have had prior therapy with an anti-PD-(L)1

pathway therapy and been deemed resistant (had progression on therapy or within 3 months of discontinuation of therapy).

e. Pancreatic:

- Histologically or cytologically confirmed metastatic pancreatic adenocarcinoma.
- Subjects has no standard therapy options available that could be of benefit as per the treating investigator.

f. Breast:

- Other than Triple-Negative Breast Cancer (TNBC):
 - Histologically or cytologically confirmed diagnosis of hormone receptor (HR) positive and/or human epidermal growth factor receptor-2 (HER-2) positive breast cancer (Allison, 2020) not amenable to curative surgery or radiation.
 - Subject has received at least 2 lines of systemic therapy in the recurrent or metastatic setting:
 - Relapse within 6 months of completing neoadjuvant/adjuvant therapy can be considered 1 line of therapy
 - Regimens may include treatments such as anthracycline, platinum or taxane chemotherapy, aromatase inhibitor, endocrine therapy, PARPi, or, if HER-2+, HER-2-targeting agent.
 - If HR⁺, must have progressed on or was offered and deferred a cyclin-dependent kinase4/6 (CDK4/6) inhibitor.

- TNBC:

- Histologically or cytologically confirmed diagnosis of triple-negative breast cancer (Allison, 2020) not amenable to curative surgery or radiation.
- Subject has received at least 1 line of systemic therapy including an anti-PD-(L)1 pathway therapy if PD-L1 Combined Positive Score (CPS) > 10. Relapse within 6 months of completing neoadjuvant/adjuvant therapy can be considered 1 line of therapy.
 - a. For subjects with CPS>10 receiving a PD-(L)1 pathway therapy, subjects must have been deemed resistant (had progression on therapy or within 3 months of discontinuation of therapy) to the anti-PD-(L)1 pathway therapy.

g. Gastric/EGJ:

- Histologically or cytologically documented locally advanced or metastatic gastric/EGJ carcinoma not amenable to curative surgery.
- Subject must have been previously treated with chemotherapy regimens based on fluoropyrimidine and platinum.
- A subject with HER-2⁺ cancer must have progressed on or was offered and deferred a prior HER-2-targeting agent and/or if known NTRK gene fusion a tropomyosin receptor kinase (TRK) inhibitor.

- Subjects with microsatellite instability-high (MSI-H) or mismatch repair deficient tumors (dMMR) or PD-L1 CPS > 5 must have had prior therapy with an anti-PD-(L)1 pathway therapy and been deemed resistant (had progression on therapy or within 3 months of discontinuation of therapy).

Protocol Number: PAL-E602-001

Version 8.0, 24 August 2023

h. Head and Neck cancer:

- Histologically or cytologically confirmed squamous or adenocarcinoma of the head and neck (oral cavity, oropharynx, hypopharynx and larynx), not amenable to local therapy with curative intent surgery or radiation therapy ± chemotherapy. Carcinomas of the nasopharynx, paranasal sinus, or salivary glands are excluded.
- Subject must have progressed on standard therapy that includes platinum-based chemotherapy and anti-PD-(L)1 pathway therapy.
 - O Subjects must have been deemed resistant (had progression on therapy or within 3 months of discontinuation of therapy) to an anti-PD-(L)1 pathway therapy.

i. Urothelial Carcinoma:

- Histologically or cytologically documented locally advanced or metastatic (Stage IV) muscle invasive urothelial carcinoma not amenable to curative surgery or radiation.
- Subject must have progressed on standard therapy that includes platinum-based chemotherapy, and/or an anti-PD-(L)1 pathway therapy.
 - Subjects must have been deemed resistant (had progression on therapy or within 3 months of discontinuation of therapy) to an anti-PD-(L)1 pathway therapy.
- Subject with known fibroblast growth factor receptor (e.g., FGFR2 or FGFR3) genetic alternations must have progressed on or was offered and deferred the standard treatments approved for these settings.
- 2. Age \geq 18 years old.
- 3. Mentally competent and able to understand and sign the informed consent form.
- 4. Eastern Cooperative Oncology Group (ECOG) performance status of 0 or 1.
- 5. Life expectancy of greater than 12 weeks per the investigator.
- 6. Subject has disease that is measurable by Response Evaluation Criteria in Solid Tumors (RECIST) v.1.1.
- 7. Female subjects of childbearing potential and male subjects are willing and able to use a highly effective method of contraception (see Appendix 10.4.2) from the first dose of study treatment through 6 months after the last dose.
- 8. Laboratory values at screening meet the following criteria:
 - a. Hematology:
 - absolute neutrophil count ≥1,500 cells/mm³
 - platelet count ≥100,000 cells/mm³
 - hemoglobin ≥9.0 g/dL without packed red blood cell transfusion within the prior 2 weeks. Prior and concomitant erythropoietin is permitted.

b. Renal:

- creatinine clearance ≥30 mL/min on the basis of the Cockcroft-Gault glomerular filtration rate estimation:

 $(140\text{-age})\times(\text{weight in kg})\times(0.85 \text{ if female})/[72\times(\text{serum creatinine in mg/dL})]$

c. Coagulation:

International Normalized Ratio (INR) and prothrombin time (PT) ≤1.5×ULN or activated partial thromboplastin time (aPTT) ≤1.5×ULN, unless undergoing anticoagulation therapy

d. Liver:

- AST and ALT $\leq 2 \times ULN$ or $\leq 2.5 \times ULN$ with liver metastasis
- Bilirubin ≤1.5×ULN, unless genetic cause of elevated bilirubin is known (such as Gilbert's Syndrome).

5.2. Exclusion Criteria

- 1. For cohorts receiving E-602 and cemiplimab combination therapy:
 - Moderate or Severe hypersensitivity to cemiplimab or any of the following excipients that are used for formulation: histidine, sucrose, L-proline, polysorbate 80.
 - Previous treatment with an anti-PD-(L)1 pathway therapy as a monotherapy and a history of ≥Grade 3 autoimmune complications or discontinuation due to toxicity, with the exception of asymptomatic Grade 3 elevations in lipase and/or amylase not associated with clinical manifestations of pancreatitis.
 - Subject has an active autoimmune disease. The following are not exclusionary: vitiligo, type 1 diabetes, autoimmune endocrinopathies that are stable on hormone replacement therapy, or psoriasis that does not require systemic treatment.
 - Previously received idelalisib.

2. Cardiovascular exclusions:

- O Subject has a medical history of an arterial thrombotic event, stroke, or transient ischemia attack within the past 12 months.
- o A medical history of symptomatic congestive heart failure (CHF) (New York Heart Association classes II-IV) or a cardiac arrhythmia that requires treatment.
- A medical history of myocardial infarction or unstable angina within 6 months before Cycle 1 Day 1.
- QTc prolongation to >470 milliseconds (ms) based on a 12-lead electrocardiogram (ECG).
- 3. History of age-related macular degeneration (AMD).
- 4. Subject has been previously administered study treatment in this study.
- 5. Subject is actively enrolled in another clinical study, unless it is an observational (noninterventional) clinical study or the follow-up component of an interventional study.
- 6. Major surgery < 4 weeks from Cycle 1 Day 1.
- 7. Use of another therapy within 4 weeks prior to Cycle 1 Day 1 or within 5 half-lives of the previous drug, whichever is shorter. Note: Subjects must have recovered from all AEs due to previous therapies to ≤ Grade 1 or baseline prior to Cycle 1 Day 1. Subjects with ≤ Grade 2 neuropathy may be eligible. Subjects with endocrine-related AEs ≤ Grade 2 requiring treatment or hormone replacement may be eligible.

- 8. Evidence of active infection requiring antimicrobials (IV or oral) within 7 days prior to Cycle 1 Day 1.
- 9. Active uncontrolled bleeding or a bleeding diathesis within 7 days before Cycle 1 Day 1.
- 10. Serious or non-healing wound, fistula, skin ulcer, or non-healing bone fracture within 7 days prior to Cycle 1 Day 1.
- 11. Subject has had a vaccine within 14 days prior to Cycle 1 Day 1.
- 12. Prior history of interstitial lung disease that required steroids or ≥ Grade 2 immune-related pneumonitis or has current non-infectious pneumonitis or interstitial lung disease.
- 13. Known human immunodeficiency virus (HIV) infection, active hepatitis B infection, or active hepatitis C infection.
- 14. Subjects with central nervous system (CNS) metastasis, and/or carcinomatous meningitis. However, subjects with CNS metastasis may participate if the subject has completed treatment of CNS metastasis and is:
 - >4 weeks from prior therapy for CNS metastasis (including radiation and/or surgery),
 - >2 weeks from receiving steroid therapy for treating CNS metastasis and are asymptomatic, and
 - o clinically stable with respect to CNS metastasis at Screening.
- 15. Subject is taking the equivalent of >10 mg/day oral prednisone or the equivalent systemic exposure by any other route of administration.
- 16. Pregnant or breastfeeding woman.
- 17. Subject is unwilling or unable to follow protocol requirements.
- 18. Subject has had an allogeneic tissue or organ transplantation or is on systemic immunosuppressive therapy.
- 19. Subject has a known additional malignancy that is progressing or has required active treatment within the past 3 years, with the following exceptions:
 - Subjects with history of basal cell carcinoma of the skin, squamous cell carcinoma
 of the skin, non-muscle invasive bladder cancer, carcinoma in situ, or localized
 breast cancer previously treated with curative intent are not excluded.
 - Localized prostate cancer that has been treated with curative intent or which does not require active treatment is not excluded.
- 20. Any condition or serious illness that, in the opinion of the investigator, would interfere with evaluation of the investigational product or interpretation of the subject's safety or study results.
- 21. History of thromboembolic event unless the event occurred > 6 months from Cycle 1 Day 1 and the subject is on anti-coagulation treatment. Note: subjects with history of thromboembolic event which occurred > 6 months from Day 1 of study treatment administration but who are not on anti-coagulation treatment may be allowed to participate if, in the judgment of the investigator, the thromboembolic event was provoked by a temporary factor that is resolved (e.g. by temporary immobility due to surgery) and the subject does not have a predisposition to or elevated risk of thromboembolic event.

22. Subject has received prior radiotherapy within 2 weeks of Cycle 1 Day 1, has a history of ≥Grade 3 radiation pneumonitis, or Grade 2 radiation pneumonitis that has been active within the last 6 months. Note: Subjects must have recovered from all radiation-related toxicities and not require corticosteroids. A 1-week washout prior to Cycle 1 Day 1 is permitted for palliative radiation (≤2 weeks of radiotherapy) to non-CNS disease.

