4.1.5. Dose-Limiting Toxicity (DLT) Definition

The DLT window of observation for the purposes of dose escalation will be Cycle 1 defined as a subject receiving 3 doses of E-602 for monotherapy cohorts and 3 doses of E-602 and 1 dose of cemiplimab for combination therapy cohorts. Any of the following events will meet the definition

of a DLT if assessed by the investigator to be possibly, probably, or definitely related to study treatment:

- Any death not clearly due to the underlying disease or extraneous causes
- Hy's law:
 - o Aspartate aminotransferase (AST) or alanine aminotransferase (ALT) >3×the upper limit of normal (ULN) AND
 - o Total bilirubin >2×ULN AND
 - o Alkaline phosphatase <2×ULN AND
 - No other reason for liver injury
- Neutropenic fever
- Any Grade \geq 3 non-hematologic toxicity (with exceptions noted below)
- Grade 4 neutropenia or thrombocytopenia >7 days
- Grade 3 thrombocytopenia with bleeding
- Grade 4 vomiting or diarrhea of any duration
- Grade 3 fatigue ≥7 days
- Grade ≥3 electrolyte abnormality that lasts >72 hours, unless the subject has clinical symptoms, in which case all Grade ≥3 electrolyte abnormality regardless of duration will be a DLT.
- For subjects with hepatic metastases, AST or ALT >8×ULN or AST or ALT >5×ULN for ≥14 days
- Recurrent Grade 3 infusion-related reaction despite pre-medication
- Grade 4 infusion-related reaction on the first occurrence
- Dose delay of >14 days for the study treatment due to an AE

However, the following AEs are NOT considered a DLT:

- Hematologic toxicity:
 - o Grade 3 anemia
 - o Grade 3 lymphopenia
 - Grade 3 or 4 neutropenia that is not associated with clinical sequelae and lasts <7 days
 - o Grade 3 or 4 thrombocytopenia without bleeding
- Cardiovascular toxicity:
 - o Grade 3 hypertension
- Other toxicities:
 - o Grade 3 fatigue lasting <7 days
 - o Grade 3 nausea/vomiting or diarrhea for less than 72 hours with adequate antiemetic and other supportive care
 - Grade 3 or higher electrolyte abnormality that lasts up to 72 hours, is not clinically complicated and resolves spontaneously or responds to conventional medical interventions
 - Grade 3 or higher amylase or lipase that is not associated with symptoms or clinical manifestations of pancreatitis

- Isolated Grade 3 infusion reaction
- AEs that are clearly and incontrovertibly due to disease progression or extraneous causes.

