6.1. Study Treatment Administered

E-602 is supplied as a sterile solution for IV infusion in glass vials. Each container is filled with 10 mL solution which contains 100 mg E-602 active ingredient in 20 mM glutamic acid-sodium hydroxide buffer with 8% (w/v) sucrose and 0.04% (w/v) polysorbate 80 at a pH value of 4.7. Cemiplimab is provided as a sterile solution (350 mg/7 ml vial) for IV infusion.

Protocol Number: PAL-E602-001

Version 8.0, 24 August 2023

For all subjects treated in the study, E-602 will be administered via IV infusion once a week at the assigned doses summarized below. For the combination therapy cohorts, 350 mg of cemiplimab will be administered via IV infusion once every 3 weeks. Subjects receiving ≥10 mg/kg of E-602 as monotherapy or in combination with cemiplimab should receive premedication including antihistamines and acetaminophen as indicated in the Pharmacy Manual. Corticosteroids should be used as premedication for subjects with previous infusion reaction(s) to E-602 as indicated in the Pharmacy Manual (see Pharmacy Manual, Section 10.5). All procedures and assessments must be completed prior to the start of dosing.

In each 21-day cycle, E-602 will be administered on Days 1, 8, and 15, and cemiplimab will be administered on Day 1. When the cemiplimab combination will be administered, cemiplimab should be administered first and E-602 administered at least 30 minutes after the cemiplimab infusion is completed. No intrasubject dose escalation of E-602 will be permitted. Details of study treatment administration methods will be provided in the Pharmacy Manual.

Cemiplimab should be administered in compliance with the manufacturer's labeling information (Libtayo® Prescribing Information 2022).

Phase 1 Treatment (Planned):

Five escalating dose cohorts of E-602 monotherapy and 2 escalating dose cohorts of combination therapy will be treated.

Cohort	Number of Subjects ^a	Dose of E-602	Frequency of E- 602	Dose of Cemiplimab	Frequency of Cemiplimab
101	3 – 6	1 mg/kg	once a week	n/a	n/a
102	3 – 6	3 mg/kg	once a week	n/a	n/a
103	3 – 6	10 mg/kg	once a week	n/a	n/a
104	3 – 6	20 mg/kg	once a week	n/a	n/a
105	3 – 6	30 mg/kg	once a week	n/a	n/a
111	3 – 6	20 mg/kg	once a week	350 mg	once every 3 weeks
112	3 – 6	to be determined	once a week	350 mg	once every 3 weeks

^a Phase 1 cohorts may be backfilled to a maximum of 15 subjects.

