- Consider giving epinephrine 0.5 mg* intramuscularly STAT. Consider repeating epinephrine at 5-minute intervals twice more as needed (i.e., if breathing becomes more labored or level of consciousness decreases).
- Consider giving oxygen if needed for dyspnea.
- Consider giving bronchodilators if indicated.
- Initiate Emergency Response Call as appropriate if subject condition warrants.
- Hospitalization may be considered as indicated for clinical sequalae.
- If isolated Grade 3, attempt to retreat on another occasion after premedication including corticosteroids using a slower infusion rate as

Infusion Reactions	Immediate Clinical Management
movement	indicated for Grade 2.
Edema/angioedema	• If Grade 4 or recurrent Grade 3, permanently
• Uncontrolled hypotension (more than 20 mmHg drop from baseline) requiring therapy	discontinue study treatment.
Severe nausea, vomiting, and/or diarrhea	
	*Note: epinephrine 1:1,000 = 1 mg/mL and
Severe (Grade 4)	epinephrine $1:10,000 = 1 \text{ mg/}10 \text{ mL}$
Life-threatening consequences: urgent intervention indicated	
*Any of the following symptoms may be observed:	
Cyanosis	
• Life-threatening hypoxia or airway compromise	
Severe angioedema (periorbital/facial)	
Altered level of consciousness	

Protocol Number: PAL-E602-001

Version 8.0, 24 August 2023

^{*}Symptoms noted are intended as potential examples at each grade. Severity grading of the infusion related reaction will be based on the investigator's judgement per CTCAE v5.0.

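### The exclusion for sucrose or polysorbate 80 hypersensitivity covers only the combination cohorts, although E-602, given to every subject, contains both

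*Protocol*

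**What the plan says.** Protocol Section 5.2, exclusion 1, opens with "For cohorts receiving E-602 and cemiplimab combination therapy". One of its sub-items is "Moderate or Severe hypersensitivity to cemiplimab or any of the following excipients that are used for formulation: histidine, sucrose, L-proline, polysorbate 80".

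Protocol Section 6.1 describes E-602 as 100 mg in 10 mL of a glutamic acid "buffer with 8% (w/v) sucrose and 0.04% (w/v) polysorbate 80". The same section gives E-602 by weekly infusion to all subjects, in monotherapy and in combination.

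Inclusion criteria 1–8 and exclusion criteria 2–22 contain no item on allergy or hypersensitivity to E-602 or its excipients. Exclusion 20, which applies to all cohorts, covers "Any condition or serious illness that, in the opinion of the investigator, would interfere with evaluation of the investigational product" and, in the rest of that sentence, interference with interpreting the subject's safety or the study results.

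On dose-limiting toxicity, Protocol Section 4.1.5 counts "Grade 4 infusion-related reaction on the first occurrence" and "Recurrent Grade 3 infusion-related reaction despite pre-medication". It lists "Isolated Grade 3 infusion reaction" among the events that do not count. For that last case Appendix 10.5 advises: "If isolated Grade 3, attempt to retreat on another occasion after premedication including corticosteroids".

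**The concern.** The sponsor has already decided that moderate or severe hypersensitivity to these two excipients is a reason not to treat. That decision is attached to cemiplimab, while the drug every subject receives contains the same two substances. A monotherapy subject with a known reaction to polysorbate 80 meets no fixed exclusion, so one site could enrol that subject and another refuse.

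What is at stake is an avoidable risk to the subject. The protocol has general safeguards:

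- premedication at 10 mg/kg and above;
- a sentinel subject in each Phase 1 cohort;
- infusion-reaction monitoring and graded management;
- rescue medication.

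These limit the harm once dosing has begun, but they do not keep the subject from being dosed. The sentinel rule is described only for Phase 1. The retreatment advice after an isolated Grade 3 reaction would also expose the subject again to the same excipients.

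There is a smaller consequence for dose finding. In an escalation cohort that is still open, a Grade 4 infusion reaction, or a recurrent Grade 3 reaction despite premedication, would be one of the two DLTs that Section 4.1.4 takes to mean that the MTD has been exceeded.

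**Working it through.** The plan states no figure on this point, so there is none to reproduce. The check compares the eligibility list with the formulation and then gives a sense of scale.

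**1. Scope of the exclusion against who is exposed**

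| Excipient named in exclusion 1 | Listed for E-602 in Section 6.1? | Fixed exclusion in combination | Fixed exclusion in monotherapy |
|---|---|---|---|
| Sucrose | Yes, 8% w/v | Yes | No |
| Polysorbate 80 | Yes, 0.04% w/v | Yes | No |
| Histidine | No | Yes | Not needed |
| L-proline | No | Yes | Not needed |

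The exclusion list runs from 1 to 22 without a gap, so the missing item is not an effect of redaction or text extraction.

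**2. Subjects a change could still reach**

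Cohorts 201–203 have 16 to 31 subjects each (Sections 6.1 and 9.4): 3 × 16 = 48 to 3 × 31 = 93. Any open Phase 1 monotherapy or backfill places would add to this, but the documents do not say how many remained at version 8.0. Section 4.3.1 reports that doses up to 10 mg/kg had been evaluated by 23 September 2022, so those escalation subjects are out of reach.

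**3. Chance of at least one affected subject in Phase 2 monotherapy**

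The documents give no prevalence *p* of moderate or severe hypersensitivity, so a range is assumed. The chance of at least one is 1 − (1 − *p*)^*n*, and the expected number is *n* × *p*.

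| Assumed *p* | At least one, *n* = 48 | At least one, *n* = 93 | Expected number, *n* = 48 to 93 |
|---|---|---|---|
| 0.01% | 0.5% | 0.9% | 0.005 to 0.009 |
| 0.1% | 4.7% | 8.9% | 0.05 to 0.09 |
| 1% | 38% | 61% | 0.48 to 0.93 |

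**4. Excipient load per weekly infusion (exposure, not risk)**

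E-602 is 100 mg / 10 mL = 10 mg/mL, with 80 mg/mL sucrose and 0.4 mg/mL polysorbate 80. For an assumed 70 kg subject, volume = dose × 70 / 10.

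| E-602 dose | Volume | Polysorbate 80 | Sucrose |
|---|---|---|---|
| 1 mg/kg | 7 mL | 2.8 mg | 0.56 g |
| 3 mg/kg | 21 mL | 8.4 mg | 1.68 g |
| 10 mg/kg | 70 mL | 28 mg | 5.6 g |
| 20 mg/kg | 140 mL | 56 mg | 11.2 g |
| 30 mg/kg | 210 mL | 84 mg | 16.8 g |

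**5. Which drug is the larger source of sucrose**

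At 20 mg/kg, three weekly E-602 infusions come to 3 × 140 = 420 mL. Cemiplimab is 7 mL (350 mg) once in the same three weeks, so the E-602 volume is 420 / 7 = 60 times larger. The cemiplimab concentrations are not in the documents. To match the sucrose in E-602 (420 × 0.08 = 33.6 g), however, its 7 mL would have to hold 33.6 / 7 = 4.8 g/mL, or 480% w/v, which is not possible. For sucrose, at least, the exclusion is tied to the smaller source.

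**The case against.** The strongest reply is that a route to exclusion before dosing already exists. SAP Section 6.2.4 says that allergies are collected with medical history at screening, so the investigator should know of a recorded allergy. Exclusion 20 has an explicit safety clause under which a known moderate or severe reaction to a component of the infused drug would plausibly fall. This stands, and it narrows the gap. It does not close it, because exclusion 20 still depends on one investigator's opinion where the combination cohorts have a fixed rule.

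The size can also be challenged. The prevalences are assumptions, the highest range comes only from the 1% value, and prevalence is probably low. The calculation counts subjects who have the hypersensitivity. The number dosed because the line is missing would be smaller, since history-taking would remove some and a rule about known hypersensitivity cannot catch unrecognised cases. All of this stands.

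Protocol Section 2.3 reports infusion reactions in 12 of 26 subjects at 10 mg/kg or more, mostly Grade 2 or lower, with one isolated Grade 3 that did not recur. Nothing attributes these reactions to excipients, and this point does not rely on their being so caused.

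The investigator's brochure and Pharmacy Manual are not available here and may carry a warning. Even so, the eligibility criteria would still treat the two arms differently.

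**Conclusion.** The point holds. The protocol states a hypersensitivity rule whose scope is too narrow for two of the excipients it names, and it gives no reason for the difference between arms.

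The consequence is a small, avoidable safety risk for monotherapy subjects. Under assumed prevalences of 0.01% to 1%, fewer than one affected subject is expected among the 48 to 93 in Phase 2 monotherapy. Sample size, power and type I error are untouched. The dose-finding consequence requires an affected subject, a Grade 4 or recurrent Grade 3 infusion reaction, and an escalation cohort still open; it cannot arise in cohorts 201–203.

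The textual finding needs no assumption. Its size depends on the prevalence, which the documents do not give. Because the correction is simple and inexpensive, it should be made despite the low expected count.

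**What to change.** For all remaining enrolment (open Phase 1 monotherapy or backfill places and cohorts 201–203), add an exclusion that applies to every cohort: known moderate or severe hypersensitivity to any E-602 excipient listed in Section 6.1, including sucrose and polysorbate 80. Leave cemiplimab, histidine and L-proline under the combination-only heading.

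The cost is one wording change in an amendment. No new procedure is needed, because the SAP already has allergies collected at screening. The downside is that a few otherwise eligible monotherapy subjects may be turned away: 0.005 (48 × 0.0001) to 0.93 (93 × 0.01) expected in Phase 2 monotherapy under the assumed prevalences.
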